4.3 Subject Recruitment and Screening

Study personnel in the Main Campus, Hillcrest and Fairview emergency rooms will be notified of all positive influenza polymerase chain reaction testing obtained in the emergency rooms. Study personnel will then screen these patients' charts for eligibility. Those patients interested in enrolling and willing to provide written informed consent will be enrolled in the study.

At Main Campus, Hillcrest and Fairview Emergency Rooms handouts explaining the study and home management of influenza will be placed where the polymerase chain reaction testing is performed. Potentially eligible patients testing positive for influenza will be given a copy of the handout by study staff or staff ordering or performing test.

The only laboratory testing required to meet inclusion criteria will be positive influenza rapid test polymerase chain reaction, and in women of childbearing potential a negative urine pregnancy test.

4.4 Early Withdrawal of Subjects

4.4.1 When and How to Withdraw Subjects

Patients may withdraw from the trial at any time and for any reason. Some possible reasons for early withdrawal include the following:

- Development of a medical condition or need for concomitant treatment that precludes further participation in the trial
- Unacceptable toxicity or any adverse event that precludes further participation in the trial
- The investigator removes the patient from the trial in the best interests of the patient
- Study completion or discontinuation
- Patient withdraws consent to continued participation in the trial

4.4.2 Data Collection and Follow-up for Withdrawn Subjects

We will continue to collect data on subjects until they are well or for 21 days if they are not entirely well only if they agree to accept our follow-up phone calls. We will call and leave messages three times before concluding a subject is truly lost to follow-up.

5 STUDY SUPPLEMENT

5.1 Description

Thick reddish-brown liquid and each 15 ml of the oral liquid contains Sambucus Nigra (Black Elderberry) fruit juice equivalent to 5.7 grams.

5.2 Supplement Regimen

Patients will be given their randomly assigned study supplement and instructed to take 15 ml orally of medication, in measuring dispenser provided, four times a day for 5 days for ages 13 and above and 15 ml two times a day for ages 5-12 for 5 days.

5.3 Method for Assigning Subjects to Supplement Groups

Treatment assignment will be made by computer generated randomization with stratification based on age 5-12 or 13 and above.

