3.2 Study Endpoints

Baseline data will be obtained at time of presentation including eligibility criteria, medical history, and current influenza symptoms.

Symptoms will be recorded using the scoring system described in a meta-analysis of "all published and unpublished Roche-sponsored randomized placebo-controlled, double-blind trials of oseltamivir treatment in adult influenza" (⁹). "The primary outcome will be time to alleviation of all symptoms. Seven influenza symptoms (nasal congestion, sore throat, cough, aches and pains, fatigue, headaches, and chills or sweats)" will be graded by severity as "absent" (0), "mild" (1), "moderate" (2), or "severe" (3). Alleviation will be defined to arise when all symptoms scored as absent or mild, and remain so for at least 21.5 hours." The secondary endpoints will be the time to alleviation and to complete resolution of individual and all symptoms. Patients will be followed daily until all symptoms have completely resolved and fever has remained less than 100° F for 24 hours, or for a maximum of 21 days if symptoms have not yet completely resolved for 24 hours.

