4 SUBJECT SELECTION AND WITHDRAWAL

4.1 Inclusion Criteria

Patients are eligible to be included in the study if they meet all of the following criteria:

- [1] Males or females \geq 5 years of age
- [2] With 48 hours or less of an influenza illness documented by polymerase chain reaction
- [3] Have AT LEAST 2 of the following 7 influenza symptoms (nasal congestion, sore throat, cough, aches and pains, fatigue, headaches, and chills or sweats) graded as either moderate or severe
- [4] Have been prescribed or offered a prescription of oseltamivir or baloxavir marboxil (Xofluza)

- [5] Have access to a phone
- [6] Subjects are capable of giving informed consent or have an acceptable legally authorized representative capable of giving consent on the subject's behalf with informed assent given by subject.

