5.8 Blinding of Study Medication

A randomization scheme will be developed via computer algorithm with stratification by age (5 to 12 years old and \geq 13 years old). Investigational pharmacy personnel not involved in patient contact or data collection directly observed and supervised by the statistician will write the numbers on the appropriate bottles of medications.

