7 STATISTICAL PLAN

7.1 Sample Size Determination

Duration of influenza was chosen as our primary outcome because previous studies described beneficial effects of elderberry extract on this outcome (1-4) and published data is available on the elderberry extract manufactured by the company supplying elderberry extract for our study to use to calculate our sample size.(3) Forty-six total influenza positive patients randomized at a 1:1 ratio with 23 active and 23 placebo patients are needed for a power of 90% to detect a mean difference in duration of illness of at least two days with a Type I error rate of 0.05, assuming standard deviations of 1.3 and 2.5 days in the supplement and placebo groups respectively.(3) Sixty-five to one hundred patients will be enrolled in our study. We are assuming a cautious estimate of nearly a 30% dropout rate.

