7.2 Statistical Methods

Study groups will be compared on duration of illness using a two-sample unequal variance t-test; the data will be transformed (such as by log-transformation) to meet distributional assumptions, and the mean

difference between groups with 95% confidence interval will be reported. Secondary analyses will assess the time to resolution of individual symptoms, and compare study groups on adherence to protocol and side effects using two-sample t-tests and Chi-square tests as appropriate. These analyses will be performed on an intent-to-treat basis. All tests will be two-tailed and performed at a significance level of 0.05. SAS 9.4 software will be used for all analyses.

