- 12. ____ Metabolic disorders (such as inherited metabolic disorders and mitochondrial disorders)*****
- 13. ____ Weakened immune system due to disease or medication (such as people with cancer, or those on 20 mg/day of prednisone or more for more than 14 days)****
- 14. ____ People younger than 19 years of age who are receiving long-term aspirin therapy
- 15. ____ People with extreme obesity (body mass index [BMI] of 40 or more)

PLEASE LIST ALL MEDICATIONS AND DOSAGES AND HOW OFTER YOU TAKE THE MEDICINE. PLEASE INCLUDE PRESCRIPTION AND OVER-THE-COUNTER MEDICATIONS INCLUDING IBUPROFEN (MOTRIN, ADVIL), ACETAMINOPHEN (TYLENOL), COLD AND FLU PREPARATIONS, AND HERBAL AND OTHER COMPLEMENTARY MEDICATIONS, VITAMINS, MINERALS AND SUPPLEMENTS

All other medical illnesses not previous recorded

Influenza vaccine statu	s up to date YES NO
If NO and <9 y.o. was	one vaccine given this year YES NO
Weight at day of presen	ntation
Highest measured temp	perature during day of presentation
Symptom Score (9):	
0=NONE or Baseline	1=MILD 2=MODERATE 3=SEVERE
Nasal congestion	
Sore throat	
Cough	
Aches and pains	
Fatigue	
Headaches	
Chills and sweats	

Symptoms are graded by severity as "absent" (0), "mild" (1), "moderate" (2), "severe" (3) Presence or absence of possible **other conditions or symptoms at baseline** AND their severity:

SYMPTOM	
SEVERITY OF SYMPTOM	
NONE=0 MILD=1 MODERA	ATE=2 SEVERE=3
BAD TASTE	
DRY MOUTH	
ABDOMINAL PAIN	
NAUSEA	
VOMITING	
DIARRHEA	
CONSTIPATION	
DIZZINESS	
HEADACHE	
RASH	
DIFFICULTY BREATHING _	
DECREASED DRINKING	
LIST ANY OTHERS WITH SH	EVERITY OF ANY SYMPTOM

VITAL SIGNS IN EMERGENCY ROOM, N/A IF ALL NOT AVAILABLE

TEMPERATURE ⁰F WEIGHT

In addition, every day patients are in the study starting from the first contact to the first day they are back to their baseline symptom level they will be asked to use the Division of AIDS (DAIDS) scale for grading the severity of adult and pediatric adverse events version 1.0, December 2004: clarification August 2009. Unlike the Symptom Score above, there are specific definitions of Grades 1-4 as outlined below.

Grade 1 Mild is defined as "Symptoms causing no or minimal interference with usual social & functional activities".

Grade 2 Moderate is defined as "Symptoms causing greater than minimal interference with usual social and functional activity".

Grade 3 Severe is defined as "Symptoms causing inability to perform usual social and functional activity".

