Grade 4 Potentially Life-Threatening is defined as "Symptoms causing inability to perform basic self-care functions OR medical of operative intervention indicated to prevent permanent impairment, persistent disability or death".

The patients will be asked to call immediately the study personnel mobile phone at [contact] for any suspected side effects at Grades 3. These patients will be referred by the principal investigator to their primary care physician, or urgent or emergency care facilities as appropriate with follow-up of their acute symptoms by the principal investigator or study coordinators until these symptoms resolve.

ATTENTION

PATIENTS WILL BE TOLD TO CALL 911 FOR ALL GRADE 4 SYMPTOMS. After their health care needs are met for Grade 4 symptoms we will ask that they please call study line for follow-up and study personnel will also keep in touch with them daily until they are well.

WRITE TIME ____AM or PM AND DATE ____OF FIRST HAVING 2 MODERATE SYMPTOMS OF INFLUENZA TIME ___AM or PM AND DATE ____FIRST DOSE OF STUDY MEDICATION GIVEN AT ENROLLMENT Guess after first dose of medication if receiving: Elderberry __OR Placebo____

CHECK TO CONFIRM PATIENTS TOLD TO KEEP ALL EMPTY AND/OR PARTIALLY FILLED STUDY MEDICATION, OSELTAMIVIR (TAMIFLU^R), OR BALOXAVIR MARBOXIL (XOFLUZA) BOTTLES FOR THE FINAL STUDY VISIT AND RETURN OF UNUSED MEDICINE IN POSTAGE PAID ENVELOPES PROVIDED AT ENROLLMENT. RECORD GUESS IF GIVEN ACTIVE OR PLACEBO MEDICATION

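### The primary t-test ignores both the age stratum and the baseline symptom score; if either predicts duration, the confidence interval is wider than it need be

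*Combined protocol and SAP*

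**What the plan says.** - Section 5.3: "Treatment assignment will be made by computer generated randomization with stratification based on age 5-12 or 13 and above". Section 5.8 repeats this: "A randomization scheme will be developed via computer algorithm with stratification by age". Neither section mentions blocks.
- Section 3.2: "Baseline data will be obtained at time of presentation including eligibility criteria, medical history, and current influenza symptoms". The form in section 14.1 grades each of the seven endpoint symptoms from 0 (absent) to 3 (severe).
- Section 4.1, on entry: "Have AT LEAST 2 of the following 7 influenza symptoms", each graded moderate or severe.
- Section 7.2, primary analysis: "Study groups will be compared on duration of illness using a two-sample unequal variance t-test". The data may be transformed, and a mean difference with its 95% confidence interval is reported.
- Section 7.1: "Forty-six total influenza positive patients randomized at a 1:1 ratio", for 90% power to detect 2 days with SDs of 1.3 (supplement) and 2.5 (placebo) days. Enrollment is 65 to 100, allowing for nearly 30% dropout.

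Sections 7.1 to 7.3 name no stratum term, no covariate and no adjusted sensitivity analysis.

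**The concern.** Age was judged important enough to stratify on, then left out of the analysis. Two separate losses can follow.

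- **Age stratum.** If age predicts duration and the arms are balanced on it, the true sampling variance of the difference no longer contains the between-age part. The t-test's standard error still does. The interval is then too wide and the test conservative.
- **Baseline severity.** The seven-symptom total can run from 4 (two symptoms at 2, the rest at 0) to 21 (seven at 3). Patients therefore start at different distances from the endpoint, which requires every symptom to be absent or mild. If that distance predicts duration, ignoring it leaves coverage correct but wastes precision.

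At stake is precision at the low end of enrollment, and power for effects smaller than the planned 2 days. Neither omission biases the estimate or inflates the type I error.

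**Working it through.** **Inputs from the documents.** SDs 1.3 and 2.5 days; difference 2 days; two-sided alpha 0.05; 23 per arm; enrollment 65 to 100; dropout nearly 30%.

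**Inputs assumed.** 30% of patients aged 5-12 (7 of 23 in each arm, balanced); R², the share of within-arm variance that age and baseline score explain together, from 0 to 30%.

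**1. The plan's own figure.** SE = √(1.3²/23 + 2.5²/23) = √(7.94/23) = 0.588 days. Satterthwaite df = 33.1 and critical t = 2.034, so the half-width is 2.034 × 0.588 = 1.20 days and the full width 2.39. Power from the noncentral t is 91.0% for 2 days; 22 per arm gives 89.7%, so 23 per arm reproduces. Power for 1.5 days is 69.8%. Dropout from 65 to 46 is 1 − 46/65 = 29.2%.

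**2. Approximate effect of adjustment.** Both SDs are multiplied by √(1 − R²), with 2 df fewer for the interval:

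| R² | √(1 − R²) | Half-width (days) | Power, 2 days |
|---|---|---|---|
| 0 | 1.000 | 1.20 | 91.0% |
| 10% | 0.949 | 1.14 | 93.6% |
| 20% | 0.894 | 1.07 | 95.8% |
| 30% | 0.837 | 1.00 | 97.7% |

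**3. Simulation.** This allows for the cost of robust standard errors in a small sample. There were 12,000 trials per setting, with covariate effects scaled to each arm's SD. The t-test is compared with least squares on treatment, age stratum and score:

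| R² | Mean CI width, t-test / HC2 / HC3 (days) | HC2 v t-test | 1.5-day power, t-test to HC2 |
|---|---|---|---|
| 0 | 2.38 / 2.39 / 2.50 | 0.3% wider | – |
| 10% | 2.37 / 2.27 / 2.38 | 4-5% narrower | 70-71% to 73-74% |
| 20% | 2.37 / 2.16 / 2.26 | 9% narrower | about 70% to 77% |
| 30% | 2.38 / 2.03 / 2.13 | 14-15% narrower | 70% to 82% |

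Power for 2 days goes from 91.0% to 90.7% at R² = 0, from 90-92% to 92-93% at 10%, and from 91-92% to 97% at 30%. An integer score from 4 to 21 in place of a normal one changes the widths by at most 0.01 day.

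**4. How strong must age be?** With a share p = 7/23 of children, an age difference D explains p(1 − p)D²/SD² of an arm's variance. For 10%, D = SD × √(0.10/0.212) = 0.69 × SD, which is 0.9 days at SD 1.3 and 1.7 days at SD 2.5. A constant 1-day age difference alone narrows the interval only from 2.38 to 2.32 days, or 2.5%.

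**5. Conservatism.** If age alone explains 10% and is balanced, the t-test rejects under the null only when a correctly scaled statistic exceeds about 2.034/0.949 = 2.14. On 33 df that has probability of about 3.9%. Simulation gives 3.5-4.1%, against 4.5-5.1% where age does not matter. HC2 rejects 4.5-5.8%.

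**6. Other settings.** At 70 evaluable (100 less 30%), power for 2 days is 98.5% unadjusted. At R² = 30% the width falls from 1.90 to 1.63 days and 1.5-day power rises from 87% to 95%. On the log scale with 46 evaluable (assumed means of 6 v 4 or 4.5 days), HC2 is 0.8-1.2% wider at R² = 0, 4% narrower at 10% and 15-16% narrower at 30%.

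**The case against.** The strongest reply is that nothing is broken. The test is valid, at worst conservative, and already has 91% power at the lowest evaluable number. The documents give no duration by age, no share of children and no correlation between score and duration, so every gain is assumed. Age would have to separate patients by 0.9 to 1.7 days to explain even 10%. The larger gains therefore lean on the baseline score, which is only a proxy because alleviation waits for the slowest symptom. With HC3 errors there is no gain at 10% and a 5% loss at 0. HC2 has slightly looser type I control: with strongly skewed (exponential) residuals on the raw scale it rejected 6.1-6.2%, against 5.3-5.8% for the t-test. No minimum number of children is set, and with one child or none the age term cannot be handled. Finally, 46 evaluable combines minimum enrollment with the full assumed dropout.

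Most of this stands as a limit on the size of the gain and on how urgent the change is. It does not remove the asymmetry: about 0.3% (raw scale) to 1% (log scale) lost with HC2 if the covariates are useless, against 4-15% gained if they explain 10-30%. The skewness point supports the transformation that section 7.2 already allows. Two children per arm gave the same widths as seven; a near-empty stratum can be met by a stated rule to drop the age term.

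**Conclusion.** The point holds as one of efficiency, not of error. The planned analysis leaves out the stratification factor and a baseline measure that is already collected. If either is prognostic, the interval is wider than necessary. At 46 evaluable the change with HC2 runs from 0.3% wider to 14-15% narrower for R² between 0 and 30%; with HC3 it runs from 5% wider to 10% narrower. The sample size of 46 is unaffected.

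These figures rest on the assumed R², on 30% children, and on balance by age within each arm, which the documents do not guarantee because they describe no blocking and dropout can disturb it. The direction is certain if a covariate is prognostic; the size is not. A time-to-event version was not simulated, so the figures do not carry over to one. The change is worth making because it costs almost nothing, and it must be prespecified, since covariates chosen after seeing the data invite selective reporting.

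**What to change.** In section 7.2, name as the primary analysis a linear model for duration on the planned (possibly log) scale. Include treatment, age stratum (5-12, 13 and above) and baseline total symptom score, with HC2 heteroscedasticity-robust standard errors. Then:

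- define the baseline total as the sum of the seven enrollment scores;
- state that the age term is dropped if a stratum has one patient or none in the analysis;
- keep the unadjusted unequal-variance t-test as a sensitivity analysis, and report results by age group descriptively;
- if a time-to-event analysis is adopted instead, stratify it by age.

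The time from "FIRST HAVING 2 MODERATE SYMPTOMS OF INFLUENZA" to the first dose, both on the enrollment form, is an optional further covariate. It is not time from illness onset, which the form does not record.

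The cost is a sentence or two of text and 2 degrees of freedom, with no new data. If neither covariate matters, the interval is about 0.3% wider (raw scale) to 1% wider (log scale) with HC2, or 5-6% wider with HC3. That is why HC2 is preferred at this sample size.

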5.4 Preparation and Administration of Study Medication

Study active and placebo medications will be prepared by PharmaCare® in Australia and mailed in 120 ml bottles with 2-3 bottles per patient of either Elderberry Extract or Placebo contained in boxes identifying the bottles in that box as either active or placebo medication.

Medications will be stored in locked areas at room temperature in a storage area in the study emergency room area with temperature monitors and daily temperature logs. Medications will be distributed by study personnel under the supervision of the Cleveland Clinic Investigational Pharmacy. The first dose of study medication will be administered by study personnel before the patients leave their presenting hospital. Subsequent doses will be administered at home by patients and their families in study provided medicine dispensers used to measure proper dosage.

5.5 Subject Compliance Monitoring

Daily phone calls will monitor the patients' symptoms, new medications or treatments, and compliance with the study medication regimen until reported complete resolution of patients' symptoms for 24 hours, or after 21 days of the study, whichever occurs first. Patients requiring follow-up pregnancy tests will have the testing performed at the Cleveland Clinic laboratory of their choice. Any patient who fails to comply with monitoring will be called three times in an effort to help with compliance with the study protocol. Patients' study medications and empty bottles remaining will be returned by stamped, addressed envelopes provided at the time of enrollment to the Main Campus based study coordinator. At that time remaining medicine will be measured prior to disposal by the investigational pharmacy.

5.6 Prior and Concomitant Therapy

All medications taken at study enrollment will be recorded on the case report forms and then into REDCap Cloud, and any changes in medications will be recorded daily throughout the study. All patients

will be discouraged from taking any cold or flu preparations except for acetaminophen and ibuprofen as needed for pain and/or fever until they have completed the study and are completely well.

5.7 Packaging

Every study patient will be given two (for patients ages 5-12 years old) or three (for patients ages 13 and above) 120 ml bottles of their study medication labeled as below:

5.8 Blinding of Study Medication

A randomization scheme will be developed via computer algorithm with stratification by age (5 to 12 years old and \geq 13 years old). Investigational pharmacy personnel not involved in patient contact or data collection directly observed and supervised by the statistician will write the numbers on the appropriate bottles of medications.

5.9 Receiving, Storage, Dispensing and Return

5.9.1 Receipt of Study Medication

PharmaCare ®will ship the product to the Cleveland Clinic investigational pharmacy.

Upon receipt of the study medication, an inventory will be performed and a medication receipt log filled out and signed by the investigational pharmacy personnel accepting the shipment. The investigational pharmacist will count and verify that the shipment contains all the items noted in the shipment inventory. Any damaged or unusable study supplement product in a given shipment will be documented in the study files. The investigator will notify study sponsor of any damaged or unusable study medication that were supplied to the investigator's site.

5.9.2 Storage

There are no special storage or handling requirements. All supplies will be stored at room temperature between 55-77° F locked in a designated storage area for each study site emergency room with temperature monitors and logs.

5.9.3 Dispensing, Return, and Destruction of Study Medications

Medications will be assigned and dispensed to each subject consecutively at the study site of enrollment.

At the completion of the study, participants are instructed to return by mail any used or unused study medication and Oseltamivir or baloxavir marboxil (Xofluza) to the CCF Main Campus. The study coordinator will perform a final reconciliation of medication dispensed, medication consumed, and medication remaining. This reconciliation will be logged in REDCap Cloud. Any discrepancies noted will be investigated, resolved, and documented prior to the destruction of any medication. All returned medications will be disposed of on site in accordance with Cleveland Clinic Pharmacy Disposition or Disposal of Investigational Drugs Policy and will be documented in the study files.

6 STUDY PROCEDURES

6.1 Pre-registration and Screening

If patients are eligible and interested in participating we will review the informed consent with them, and their families if necessary, and obtain written informed consent or assent, depending upon patients' ages.

6.2 Visit 1

Visit 1 will be completed at the same visit for registration and screening. A nasopharyngeal swab will be obtained for Roche^R cobas^R Liat^R PCR assays for influenza A&B prior to enrollment in study to confirm all study patients have documented influenza.

Informed consent, and assent when indicated, will be obtained prior to completing any study related assessments. Eligibility for the study will be confirmed and baseline data will be obtained.

All women of childbearing potential will have a urine pregnancy test before starting and upon completion of the study. Pregnancy tests will be done following standard Cleveland Clinic operating procedures and documented in the electronic medical record, the case report forms and REDCap Cloud. The result of the pregnancy test(s) will be disclosed to the minor subject and their parent(s)/legal guardian.

Patients will be instructed on how to return unused study medication in the provided stamped envelope addressed to the study coordinator, and for women of childbearing potential how to obtain an end of study pregnancy test at the most convenient Cleveland Clinic laboratory.

Patients will be given their randomly assigned study medication and instructed to give 15 ml of medication, in a measuring cup provided, 4 times a day for 5 days for ages 13 and above and 15 ml 2 times a day for ages 5-12 for 5 days. They will be given their first dose of study medication prior to leaving the emergency room.

Patients will be asked to please avoid taking any additional cold or influenza medications if possible. They will be told they may take ibuprofen or acetaminophen for pain or fever. They will be asked to report daily all medications taken not reported on their day 1 visit. Taking additional medications will not disqualify patients from the study other than taking prescription antibiotics or antivirals prior to the start of the study.

Patients will receive daily phone calls to remind them to take each dose of their study medication and to answer their daily surveys (see Appendix 1). All patients who do not answer their daily surveys on the first call, will receive two additional phone call attempts to have the survey answered.

6.3 Visit 2, etc.

After the initial in-person study visit at the time of enrollment, all subsequent visits will be by telephone. As previously outlined, women of childbearing potential will have an end of study urine pregnancy test to be arranged at a nearby Cleveland Clinic Laboratory.

Study Assessments

Procedure	Screening/Baseline Visit One	Daily Phone Call Until Well	Final Study Visit
Confirm Inclusion/Exclusion Criteria	Х		
Obtain Informed Consent	Х		
Nasopharyngeal swab for PCR test for influenza A&B, RSV	Х		
Urine Pregnancy Test for Women of Childbearing Potential	Х		Х
Screening/Enrollment Questionnaire	Х		
Dispense Study Medication	Х		
Daily (Symptom) Questionnaire	Х	Х	Х
Record Side Effects/AE/SAE		Х	
Study Drug Return			Х

Laboratory Procedures

Roche^R cobas^R Liat^R PCR assays for influenza A&B and RSV on day of entry into study. This is CLIA waived testing.

Urine pregnancy testing initially will be done using a point of care pregnancy test per standard Cleveland Clinic procedures. The end of study pregnancy testing will be done per usual protocol at Cleveland Clinic outpatient laboratories.

